#### 1. Light-based treatment protocol

The Eye-light unit (Espansione Group Ltd, Funo, Italy) was used to deliver the light-based therapies. Prior to the intense pulsed light therapy (IPL), the highest meiboscore of either eyelid and the Fitzpatrick skin grading was inputted into the unit system. This automatically calibrated the optical radiance output of the IPL. Table 1 details the exact output for each combination of settings.

**Table 1.** Optical radiance output of the intense pulsed light (IPL) therapy of the Eye-light unit (Espansione Group Ltd, Funo, Italy) according to inputted grading from the meiboscale and Fitzpatrick skin grading.

Pult Meiboscale	Fitzpatrick skin grading	Optical radiance output (J)
1	1	59
	2	59
	3	59
	4	59
2	1	60
	2	62
	3	62
	4	60
3	1	62
	2	66
	3	66
	4	64
4	1	65
	2	69
	3	69
	4	67

Figure 1 demonstrates the light-based treatment administration protocol used in this clinical trial for four treatment sessions.

**Figure 1.** Intense pulsed light (IPL) protocol with (A) sequential placements of treatment cartridge for the five different regions involved, and (B) sham IPL placement of a disconnected empty cartridge along the same five different regions on the contralateral side but with the working IPL cartridge pointed away from the patient's face to simulate a pulse. Low-level light therapy (LLLT) was then administered for 15 minutes (C) with placement of the mask consisting of a series of red light-emitting diodes (LEDs). These were conducted with the Eye-light unit (Espansione Group Ltd, Funo, Italy).

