**Table 2. The sequence of assessments for each visit**

Procedures	Visits					
	1	2	3	4	5	6
Screening with inclusion and exclusion criteria	✓					
OSDI, DEQ5 and adapted SANDE questionnaires	✓	✓	✓	✓	✓	✓
General medical and ocular history, and lifestyle questions	✓	✓	✓	✓	✓	✓
Visual acuity assessment	✓	✓	✓	✓	✓	✓
Oculus Keratograph 5M, Part 1	✓	✓	✓	✓	✓	✓

 
- Number of total and partial blinks in 30 s
 
- Tear meniscus height
 
- Non-invasive tear break up time
 
- Lipid layer pattern
 
- Bulbar and limbal hyperaemia grading
 
						
Laser Doppler flowmetry and multimodal spectroscopy at central lower eyelids	✓				✓	✓
Slit lamp biomicroscopy	✓	✓	✓	✓	✓	✓

 
- Telangiectasia grading
 
						

Procedures	Visits					
	1	2	3	4	5	6

 
- Number of blocked or capped Meibomian gland orifices
 
- Demodex detection (2 lashes randomly chosen on either lid and assessed with lateral traction method)
 
- Meibomian gland expression with Korb expressor
 
						
Oculus Keratograph 5M, Part 2	✓	✓	✓	✓	✓	✓

 
- Fluorescein sodium and lissamine green staining grading on ocular surface and lid wiper epitheliopathy
 
						
Meibography	✓				✓	✓
In-vivo corneal confocal microscopy	✓				✓	✓

The following provides further details the instrumentation or procedures involved:

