**iii. Oculus Keratograph 5M, Part 1 (Optikgerlite GmbH, Wetzlar, Germany)**

Number of total and partial blinks in 30 seconds, tear meniscus height measured using in-built calipers in the Oculus Keratograph 5M software (average of 3 measures), objective non-invasive tear break up time (average of 3 measures), subjective lipid layer pattern grading (1: Open meshwork; 2: Closed meshwork; 3: Wave pattern; 4: Amorphous pattern; 5: Colour fringe pattern) [4], and automated bulbar conjunctiva and limbal redness grading (0: none to 4: severe in 0.1 increments) were assessed using this instrument.

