## Statistical Analysis

Two-factor repeated measures analysis of variance (ANOVA) was used for statistical analysis to assess changes over time across the multiple visits between each treatment group. One-way repeated measures ANOVA was used to assess changes over time for overall measures including OSDI scores, DEQ-5 scores, visual acuity, and blink rate. The Greenhouse-Geisser correction was applied to the one-way and two-factor repeated measures ANOVA results to adjust for the lack of sphericity. Paired t-test for normally distributed data or Wilcoxon signed-rank test for non-normally distributed data was used to assess differences between the two treatment modalities within the same visit.

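### Does the treatment-by-visit ANOVA of tear break-up time need an alternative for non-normal data?

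*Combined protocol and SAP*

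**What the plan says.** The Statistical Analysis section sets the test of a different course over time: "Two-factor repeated measures analysis of variance (ANOVA) was used for statistical analysis to assess changes over time across the multiple visits between each treatment group". The one adjustment attached to it is stated as follows: "The Greenhouse-Geisser correction was applied to the one-way and two-factor repeated measures ANOVA results to adjust for the lack of sphericity". For the comparison of the two modalities at a single visit there are two options: "Paired t-test for normally distributed data or Wilcoxon signed-rank test for non-normally distributed data was used".

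The section on the light-based treatment protocol (Figure 1) places the sham "along the same five different regions on the contralateral side", so treatment is a factor within the participant. Table 2 lists "Non-invasive tear break up time" at Visits 1 to 6, and the description of Keratograph Part 1 makes each value the mean of three readings. The text gives no sample size, alpha, SD or error shape for this outcome and does not name it as primary.

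**The concern.** The section foresees non-normal data and provides for it in one place only. The paired within-visit comparison can switch to a rank test; the two-factor ANOVA cannot. Greenhouse-Geisser adjusts for lack of sphericity and says nothing about the shape of the errors. The within-visit Wilcoxon test does not fill the gap, because it does not test change over time.

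Break-up time is where this could matter most. It cannot be negative, may be right-skewed, and may vary more when it is long. A few large side differences could then dominate the ANOVA error term and hide a real difference in course between IPL+LLLT and sham IPL+LLLT. At stake would be power for that one test on that one outcome.

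**Working it through.** **What the test works on.** Let D(i,t) be the difference between the two sides of participant i at visit t. With two sides, the treatment-by-visit test is a one-way repeated measures F test on D:

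F = [n Σ_t (D̄_t − D̄)² / (k−1)] / [Σ_i Σ_t (D_it − D̄_i − D̄_t + D̄)² / ((n−1)(k−1))]

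Here k = 6 visits. At an assumed n = 30 the degrees of freedom are 5 and 29 × 5 = 145, both multiplied by the estimated Greenhouse-Geisser epsilon. Two things follow:
- The participant's own level cancels, so a skewed spread of break-up times across participants does not by itself harm the test.
- If both sides have the same error distribution, D is symmetric about its centre even when the times are skewed. What can remain is heavy tails, which cost power.

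**False positives.** The documents give no figure to reproduce, so everything below is simulation with assumed inputs and alpha 0.05. At n = 12, 20, 30 and 60 the planned test rejected a true null in 1 to 5% of runs, including when both eyes improve equally by 40 to 100%. A separate set with normal, gamma, exponential and log-normal errors (n = 20 to 40, 3 or 6 visits) gave 2 to 5%. The planned test is not anti-conservative here.

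**Power.** The comparator takes D, subtracts the participant's mean D over visits, ranks all values together (30 × 6 = 180) and applies the same F test. Inputs for n = 30, with 4000 runs per setting (Monte Carlo SE at most √(0.25/4000) = 0.8 points):
- Log-normal: median 8 s; participant/eye/visit log-SDs 0.4/0.2/0.35, 0.5/0.2/0.45 and 0.6/0.3/0.5; side effect 0, 0.25, 0.5, 0.75, 1, 1 times log 1.4.
- Near normal: mean 8 s; SDs 2/1/1.5, 2/1/2 and 2.5/1/2.5; gains of 1.2, 1.6 and 2.0 s.

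| Error model | Planned ANOVA | Aligned rank | Difference (points) |
|---|---|---|---|
| Log-normal, uncapped | 59, 30, 18% | 70, 44, 32% | +11, +14, +14 |
| Log-normal, capped at 24 s | 66, 39, 29% | 69, 41, 31% | +3, +2, +2 |
| Near normal, additive | 51, 50, 51% | 51, 49, 49% | 0, −1, −2 |

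A repeat run gave 61/71, 29/44 and 19/34% uncapped and 66/69, 38/41 and 29/31% capped. With skewed participant levels but additive errors, power was 72 to 75% for the planned test and 71 to 74% for ranks, as the cancellation above predicts. Logging is no safe substitute: under near-normal errors it gave 36, 32 and 30%, against 51, 50 and 51% for the planned test.

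**Where ranks do worse.**
- Correlated visit errors (AR(1), 0.5): −3 points.
- Additive errors with only a fifth to a half of participants responding: −1 to −5 points.
- Log-normal errors with only the third with the longest times responding: −10, −5 and +2 points; a repeat of this kind of case gave 42% against 35%, so 42 − 35 = 7 points lost.
- Equal means, but the treated eye's log-SD doubling over the visits: at n = 60 the rank test rejected in 8 to 10% of runs, against 3 to 4% for the planned test. With equal means and unequal log-SDs the medians differ, and ranks respond to that. The rank test therefore answers a different question from a comparison of means.

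**Other outcomes.** For simulated 0–3 and 0–4 grades the two tests agree within 1 point (52 v 51, 24 v 24, 58 v 57%).

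**The case for a change.** The asymmetry in the section is real: no transformation, rank method or residual check is named for the ANOVA, although non-normal data are foreseen two sentences later. Heavier tails also give larger gains than the table shows. In the separate set of simulations (n = 30, six visits, a side difference of 0.73 error SD), power rose from 42% to 69% with exponential errors and from 43% to 95% with log-normal errors of log-SD 1.0. The cost under normal errors was only 1 to 3 points where the planned test had 66 to 92% power. Used as a labelled sensitivity analysis beside the planned ANOVA, ranks would carry almost no risk.

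The textual observation and the conditional gain both stand. The size of the gain does not carry over to this trial. Each recorded value is a mean of three readings. If the skew lies in the single reading, averaging shrinks the gain to 42 v 49% (exponential) and 43 v 47% (log-normal, log-SD 0.5), though it stays large at log-SD 1.0 (44 v 79%). If the log-normal variation lies between visits, averaging leaves 9 to 15 points uncapped, but 0 to 3 with a 24 s cap. Nothing in the documents says which of these holds. An optional sensitivity analysis on one outcome not named as primary leaves the planned result as it is.

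**Conclusion.** The concern does not hold. The planned test of break-up time did not over-reject under the skewed error models tried, and no stated number, rule or property of the plan is shown to be wrong. What is left is a comparison of power between two defensible tests. At n = 30 it runs from about +14 points for ranks (log-normal, uncapped), through +2 to +3 (capped at 24 s) and 0 to −2 (additive), to −10 (only the longest times responding). Letting ranks lead would also replace a comparison of means by a test of shift, with up to 8 to 10% rejection of equal means at n = 60 when spread differs markedly by side and visit. Reasonable statisticians would choose differently.

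The section is written in the past tense, so the analysis may already be done; a change of lead test would then be post hoc. All figures rest on assumed n, SDs, effects and error shapes. The conclusion does not depend on their exact values: it rests on the type I error results and on the absence of any evidence of skew in the documents.

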## 2. Ocular assessment schedules and details

The study was structured into multiple visits and all conducted at the Aston Dry Eye Clinic in Aston University, Birmingham, United Kingdom. Each visit lasted for about 1.5 hours, with the sequence of assessments detailed in Table 2:

- Visit 1: Screening ± First treatment session
- Visit 2 (2 to 3 weeks after Visit 1): Second treatment session
- Visit 3 (2 to 3 weeks after Visit 2): Third treatment session
- Visit 4 (2 to 3 weeks after Visit 3): Fourth and final treatment session
- Visit 5 (2 weeks after visit 4): First follow-up
- Visit 6 (3 months after visit 4): Second and final follow-up

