**i. OSDI and DEQ5 questionnaires**

These are validated questionnaires used to assess the severity and frequency of the dry eye symptoms experienced by the participants. OSDI consists of 12 questions regarding the frequency of symptoms and impact of daily activities over the past week. The scores range from 0 to 100 [1]. The DEQ5 assesses the severity and frequency of the discomfort, dryness and wateriness during a typical day in the past month. The scores range from 0 to 22 [2]. The adapted SANDE questionnaire is a visual analogue scale quantifying the severity and frequency of dry eye symptoms for each eye separately from 0 to 100 [3]. These were self-administered by the patient on a printed A4 sheet of paper.

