**iv. Laser Doppler flowmetry**

This is an instrument developed by the Aston Institute of Photonics Technology (Aston University, Birmingham, United Kingdom) which uses a small probe lightly touching the skin to analyse blood flow in small vessels [5, 6]. This was adapted and mounted on the slit lamp to assess the blood flow of the external cutaneous skin of the central lower eyelid of each side.

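### Optional gain in precision: for outcomes that are approximately normal or can be transformed, adjust the side comparisons at Visits 5 and 6 for the Visit 1 side difference

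*Combined protocol and SAP*

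**What the plan says.** The caption of Figure 1 (Light-based treatment protocol) makes the comparison within-person: IPL on one side and "sham IPL placement of a disconnected empty cartridge along the same five different regions on the contralateral side", followed by LLLT.

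The Statistical Analysis section has three parts:

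- A two-factor repeated measures ANOVA "to assess changes over time across the multiple visits between each treatment group".
- A one-way repeated measures ANOVA for "changes over time for overall measures including OSDI scores, DEQ-5 scores, visual acuity, and blink rate". These are treated as patient-level and are outside this point.
- A paired t-test, or a Wilcoxon signed-rank test if the data are not normal, to "assess differences between the two treatment modalities within the same visit".

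No covariate or change score is named for the third part. That it uses each visit's unadjusted values is an inference from this silence, though it is the plain reading.

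Table 2 schedules every measure at Visit 1 that it repeats at Visits 5 and 6, for example "Laser Doppler flowmetry and multimodal spectroscopy at central lower eyelids". Side-level measurement is explicit for the adapted SANDE, a "visual analogue scale quantifying the severity and frequency of dry eye symptoms for each eye separately from 0 to 100", and for laser Doppler flowmetry, used to "assess the blood flow of the external cutaneous skin of the central lower eyelid of each side". The visit list gives "Visit 5 (2 weeks after visit 4): First follow-up" and puts Visit 6 three months after Visit 4. Visit 1 is the screening visit, at which the first treatment may or may not also be given.

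**The concern.** The same-visit comparison is the only planned analysis that can give a treatment difference at a named visit. The Background asks about short-term and long-term change, so the contrasts at Visit 5 and Visit 6 matter most. If one side of a participant's face tends to be worse than the other and stays so, part of the spread in the later side difference was already visible at Visit 1. Removing it would tighten the estimate with data already in hand.

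The two-factor ANOVA does not do this. If Visit 1 is a level of time, its treatment-by-visit interaction cancels persistent side differences, but it is an omnibus test and gives no estimate at Visit 5 or Visit 6.

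What is at stake is precision at those visits. How much depends on quantities that the supplied text does not give.

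**Working it through.** **Inputs.** The within-person design, the Visit 1 measures and the same-visit tests come from the sections cited above. The plan gives no sample size, alpha, SD, effect or correlation, so there is no figure of its own to reproduce. Assumptions: n = 20 to 40 participants, two-sided alpha 0.05, a true shift of 0.5 SD of the side difference, and r from 0 to 0.7.

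**Set-up.** Let D1 and D5 be the side differences (IPL+LLLT minus sham IPL+LLLT) at Visit 1 and at Visit 5; Visit 6 is treated in the same way. The planned paired test estimates the mean of D5. The alternative regresses D5 on D1, uncentred, and takes the intercept, which is the expected side difference when the sides start level.

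**Precision, normal data with mean D1 = 0.** Variance of the intercept relative to the unadjusted mean:

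(1 − r²)(n − 2)/(n − 3)

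Setting this to 1 gives break-even r = 1/√(n − 2): 1/√18 = 0.24, 1/√28 = 0.19 and 1/√38 = 0.16 at n = 20, 30 and 40.

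At n = 30, (n − 2)/(n − 3) = 28/27 = 1.037. The width column also includes the lost degree of freedom. Power is from simulation.

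| r | Variance factor | 95% CI width | Unadjusted power | Adjusted power |
|---|---|---|---|---|
| 0 | 1.00 × 1.037 = 1.037 | +2% | 75% | 74% |
| 0.3 | 0.91 × 1.037 = 0.944 | −3% | 75% | 78% |
| 0.5 | 0.75 × 1.037 = 0.778 | −12% | 75% | 85% |
| 0.7 | 0.51 × 1.037 = 0.529 | −27% | 75% | 95% |

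At n = 20, unadjusted power is 56%, and adjusted power is 54%, 58%, 66% and 82% at the same four values of r. Type I error stayed near 5% for both methods.

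**Two variants to avoid.**

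- Centring D1 at its sample mean returns the unadjusted mean with a standard error that is too small. At n = 20, type I error was 8.6% at r = 0.5 and 15.2% at r = 0.7.
- A change score D5 − D1 has variance factor 2(1 − r), so it beats the unadjusted test only if r exceeds 0.5.

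**What r might be.** If values from the same eye correlate at s across visits, the two eyes correlate at b, and there is no shared visit noise, then r = (s − b)/(1 − b).

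- s = 0.7, b = 0.6: 0.1/0.4 = 0.25
- s = 0.7, b = 0.4: 0.3/0.6 = 0.50
- s = 0.7, b = 0.2: 0.5/0.8 = 0.62
- s = 0.5, b = 0.4: 0.1/0.6 = 0.17, just below break-even at n = 30

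**Skewed outcomes (log-normal, n = 30).** Power of the planned Wilcoxon test against the regression on untransformed values:

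| Log-SD (assumed) | Observed r | Wilcoxon | Untransformed regression |
|---|---|---|---|
| 0.8 | 0.15 / 0.27 / 0.42 / 0.63 | 67–69% | 59 / 62 / 67 / 82% |
| 1.0 | 0.1 / 0.27 / 0.4 / 0.6 | 66–67% | 51 / 54 / 59 / 72% |

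The largest loss is 66 − 51 = 15 points, and break-even lies at about r = 0.4 or above. On logs, the regression had 76–85% power when the observed r was about 0.13 to 0.42. Not all of that is due to adjustment: an unadjusted paired t-test on logs is the normal case above, with 75%.

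**The planned interaction test.** With a constant effect after treatment and n = 30, its power at r = 0.3, 0.5 and 0.7 is 63%, 79% and 95% for measures taken at Visits 1, 5 and 6. It is 56%, 73% and 94% for measures taken at all six visits.

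**The case against.** The best argument against acting is that the benefit rests on unknowns. Pairing the two sides already removes person-level variation, so r may be small. Visit 6 falls about 19 to 22 weeks after Visit 1 (three gaps of 2 to 3 weeks, then about 13 weeks), with four treatments since the Visit 1 assessments, which may weaken the correlation further. This stands, and it is why the gain can only be given as a range.

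The gain over the whole plan is also smaller than the gain over the paired test alone. Taking the better planned test for three-visit measures at n = 30, the comparison with the adjusted test is 75% against 78% at r = 0.3, 79% against 85% at r = 0.5, and 95% against 95% at r = 0.7. This stands too. At high r, what remains is mainly a tighter estimate at a named visit.

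A reader might infer that every continuous outcome should move to the regression. The documents do not support that, because they provide for non-normal data through the Wilcoxon test. Tear break-up time, blood flow and immune-cell density may well be skewed, and on such data an untransformed regression can do worse than the plan.

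Finally, the section is written in the past tense, and the supplied text names no primary outcome or multiplicity rule. A second set of results across many outcomes could invite selection. That is a reason for clear labelling and for showing both analyses, and not a reason against the estimate itself.

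**Conclusion.** The point holds as an optional improvement, to be considered. The plan names no Visit 1 adjustment for the same-visit comparisons, the data for it are scheduled, and the omnibus interaction does not supply an estimate at Visit 5 or Visit 6. For approximately normal or suitably transformed outcomes at an assumed n = 30, the interval is about 3% to 27% narrower for r between 0.3 and 0.7. There is no gain at r of about 0.2 and a small loss below it.

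This rests on three things the supplied text does not settle: the values of n and r; that the IPL side was chosen without regard to severity; and that Visit 1 values were taken before treatment. On the last, the treatment protocol needs the meiboscore before IPL, which supports a pre-treatment reading for meibography but does not state it for every measure.

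A reader might infer that the planned paired tests are biased or invalid because they leave out baseline. The documents do not support this: if sides were allocated at random, those tests are valid, and only precision is at issue. Nor do the documents show that the trial lacked power, since they give no sample size or target effect.

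**What to change.** - **Approximately normal side-specific continuous outcomes, or skewed ones after a log or similar transformation.** Regress the between-side difference at Visit 5, and separately at Visit 6, on the Visit 1 between-side difference, uncentred. Report the intercept with its 95% confidence interval and the observed r, beside the planned test. Any transformation is applied to each side's values before differencing.
- **Ordinal grades** (telangiectasia, Oxford staining, meiboscale) **and non-normal outcomes that no transformation fixes.** Keep the planned Wilcoxon test as the main test. A permutation test of the same intercept, swapping the two sides jointly at Visit 1 and the later visit, may be added as support.
- **Conditions to state.** Say how the IPL side was chosen, because both the intercept and the permutation test need a choice unrelated to severity. Confirm that Visit 1 values are pre-treatment.
- **Label.** If the data have been seen, call the adjusted analysis post hoc.

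Cost: no new data, one degree of freedom per comparison, and about 1 to 3 power points if r is below about 0.2. The permutation test, if used, needs a short program. Applying the regression to untransformed skewed data would cost far more, which is the reason for the restriction.
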